OnCore	Online Collaborative Research Environment, clinical trial management software
PI	Principal Investigator
QA	Quality Assurance
QC	Quality Control
SAE	Serious Adverse Event
SMS	Study Monitoring Service

[figure not shown]
1. Study Summary

Envarsus XR in Delayed Graft Function (E-DGF)	
Short Title and Precis	Envarsus in DGF (E-DGF)
Protocol Number	2018-0530
ClinicalTrials.gov number	NCT03864926
Phase	Phase IV
Methodology	Single center, open randomized trial
Study Duration	2.5 years
Study Center(s)	Single Center
Objectives	Envarsus XR is an extended release tacrolimus designed to deliver tacrolimus more consistently, thus avoiding large fluctuations of tacrolimus trough levels with Envarsus XR compared to immediate release tacrolimus. It is expected that patients with DGF on Envarsus XR will have more stable tacrolimus levels and facilitate early recover from DGF compared to immediate release tacrolimus.
Number of Subjects	Total of 100, 50 in each arm
Diagnosis	Kidney transplant recipients with the diagnosis of DGF
Main Inclusion Criteria	New kidney transplant recipients with DGF transplanted at UW hospital
Main Exclusion Criteria	Multi-organs transplant recipients Patients not on or not planned to be on tacrolimus based regimen after transplant Complications requiring allograft nephrectomy
Study Product, Dose, Route, Regimen	Per UW Abdominal Transplant Immunosuppression Management Adult-Inpatient/Ambulatory Clinical Practice Guideline: immediate release tacrolimus (generic) 0.05 to 0.1 mg/kg/day in two-divided dose by mouth will be used in all patients after kidney transplant as the standard of care (SOC). All subject will receive at least one dose of SOC tacrolimus. Extended release Envarsus XR (study drug) 80% of the total daily dose of SOC tacrolimus or close to the available strength of 0.75 mg, 1 mg and 4 mg tablet as a single tablet or combination of two or more tablets of Envarsus XR once a day by mouth will be used in the study arm and SOC immediate release tacrolimus will be continued in the SOC arm.
FDA status of product	IND Exempt Determination
Duration of administration	Until recovery of DGF to a maximum of 3 months
Reference therapy	Immediate release tacrolimus
Statistical Methodology	Data Analysis: Descriptive statistics for the data will be compiled. Any trends for differences between two groups for the composite endpoints will be assessed.

Figure 1: Schematic of Study Design**Flow diagram:**

Prior to enrollment

Total 100 patients: Obtain informed consent. Screen potential subjects by inclusion and exclusion criteria, review labs and documentation. All patients will have received or will be receiving immediate release tacrolimus as standard of care (SOC)

Visit 1 (Diagnosis of DGF)

Perform baseline assessments.
Medical records and the Transplant Database will be reviewed for the following: Routine blood test, urine test and other radiological investigation based on the clinical judgment. Commonly used test include: CBC, Lyses, BUN, Creatinine, glucose, urinalysis, urine protein/creatinine, immunosuppressive level

Visit 2 (Diagnosis of DGF)

Randomize into Tacrolimus (SOC) or Envarsus XR (study) group

Visit 3 (Daily while inpatient
Or in clinic visit)

Medical records and the Transplant Database will be reviewed for the following: Follow up assessments of study endpoints and safety.
Evaluate for need of dialysis or not. Review routine blood test performed in the morning along with urine output in last 24 hours and examinations to assess the

Visit 4 (recovery from DGF)

Medical records and the Transplant Database will be reviewed for study endpoints and safety, Routine blood test performed, H&P documenting discharged from the DGF clinic

Visit X (Time Point)

Medical records and the Transplant Database will be reviewed for the following:
Interval between transplants to the recovery of DGF
Interval between first and last dialysis
Total number of dialysis
Total number of tacrolimus or Envarsus XR dose adjustment required

2. Key Roles

2.1. *Investigator and Study Center:*

[name], MBBS
Assistant Professor (CHS)
Department of Medicine-Nephrology
[name]
[name]
[name]
[name]
[contact]
Email: [contact]

Principal Investigator:

University of Wisconsin Hospital and Clinics
[name]
[name]

Participating sites:

UW Health-University of Wisconsin Hospital and Clinics
Clinical Laboratories
[name]
[name]

Local Laboratory Services:

[name]
[name]
School of Medicine and Public Health
[name]
Email: [contact]

**ICTR Data Monitoring
Committee Contact:**

[name]
School of Medicine and Public Health
[name]
Ph: [contact]

**ICTR Study Monitoring
Service Contact:**

Veloxis Pharmaceuticals, Inc
[name],
[name]
[contact]
[contact]
www.veloxis.com

Funding Sponsor:

3. Background and Introduction

This document is a clinical research protocol for a human subjects study. This study is to be conducted according to the US and international standards of Good Clinical Practice (FDA Title 21 part 312 and International Conference on Harmonization guidelines), applicable government regulations and Institutional research policies and procedures.

3.2. Hypothesis

With extended release Envarsus XR, designed to deliver tacrolimus more consistently, it is hypothesized that there will be less fluctuation of tacrolimus levels requiring less dose adjustment and ultimately early recovery of the DGF.

3.3. Study Agent

Tacrolimus is a macrolide immunosuppressant produced by *Streptomyces tsukubaensis*. Chemically, tacrolimus is designated as [3S-[3R*[E(1S*,3S*,4S*)], 4S*,5R*,8S*,9E,12R*,14R*,15S*,16R*,18S*,19S*,26aR*]-5,6,8,11,12,13,14,15,16,17,18,19,24,25,26,26a-hexadecahydro-5,19-dihydroxy-3-[2-(4-hydroxy-3-methoxycyclohexyl)-1-methylethylene]-14,16-dimethoxy-4,10,12,18-tetramethyl-8-(2-propenyl)-15,19-epoxy-3H-pyrido[2,1-c][1,4]oxaazacyclotricosine-1,7,20,21(4H,23H)-tetrone, monohydrate. Tacrolimus has an empirical formula of C44H69NO12•H2O and a formula weight of 822.03. Tacrolimus appears as white crystals or crystalline powder. It is practically insoluble in water, freely soluble in ethanol, and very soluble in methanol and chloroform.

Tacrolimus (generic; immediate release) is FDA approved for the prophylaxis of organ rejection in heart, kidney and liver transplant recipients.

Envarsus XR is FDA approved for the prophylaxis of organ rejection in kidney transplant recipients converted from tacrolimus immediate-release formulations, in combination with other immunosuppressants. Envarsus XR, is designed to deliver tacrolimus more smoothly over the whole day.

Envarsus XR, a calcineurin-inhibitor immunosuppressant, is available for oral administration as extended-release tablets containing the equivalent of 0.75 mg, 1 mg, or 4 mg of anhydrous tacrolimus USP. Inactive ingredients include hypromellose USP, lactose monohydrate NF, polyethylene glycol NF, poloxamer NF, magnesium stearate NF, tartaric acid NF, butylated hydroxytoluene NF, and dimethicone NF. Tacrolimus is the active ingredient in ENVARSUS XR.

Note: extended release products (Envarsus XR) are not interchangeable or substitutable with immediate release tacrolimus.

3.4. Summary of Relevant Preclinical Data

The FDA approval of Envarsus XR was based on a conversion study (11). The conversion study was a randomized, open-label, multinational study evaluating once daily Envarsus XR when used to replace immediate-release tacrolimus administered twice daily for maintenance immunosuppression to prevent acute allograft rejection in stable adult kidney transplant patients. Patients who received a kidney transplant 3 months to 5 years before study entry and on a stable dose of tacrolimus immediate-release of at least 2 mg per day and tacrolimus whole blood trough concentrations between 4 and 15 ng/mL were randomized to 1) switch from twice daily tacrolimus immediate-release to once daily Envarsus XR (N=163) or 2) continue tacrolimus immediate-release twice daily (N=163). Mycophenolate mofetil (MMF) or mycophenolate sodium (MPS), or azathioprine (AZA) and/or corticosteroids were allowed as concomitant immunosuppressants during the study period according to the standard of care at the participating site. In the conversion study, stable kidney transplant patients converted to Envarsus XR at an average daily dose that was 80% of their tacrolimus immediate-release daily dose prior to conversion. Mean tacrolimus whole blood trough concentrations were maintained within a relatively narrow range throughout the duration of the study for both the Envarsus XR conversion group and the tacrolimus immediate-release continuation group. At week 1 (after 7 days of stable dosing), the mean \pm SD tacrolimus trough concentrations were 7.2 ± 3.1 ng/mL for the Envarsus XR conversion group and 7.7 ± 2.5 for the tacrolimus immediate-release continuation group; the baseline values were 7.8 ± 2.3 , and 8.0 ± 2.3 , respectively. The average daily mycophenolate equivalent doses in the conversion study were comparable between the Envarsus XR and tacrolimus immediate-release treatment groups. The efficacy failure rates including patients who developed biopsy proven acute rejection (BPAR), graft failure, death, and/or lost to follow-up at 12 months, as well as the rates of the individual events were essentially the same between the tacrolimus immediate-release and tacrolimus extended-release groups (Envarsus XR).

In another large randomized control trial (12), once a day Envarsus XR in new kidney transplant recipients had a comparable efficacy and safety profile compared to that of immediate release twice a day tacrolimus even at 24% lower total dose suggesting Envarsus XR to have better absorption and bioavailability. In another, Phase III randomized trial, Envarsus XR achieved target tacrolimus trough levels more rapidly compared to twice daily tacrolimus group (13).

Envarsus XR is a calcineurin-inhibitor immunosuppressant indicated for the prophylaxis of organ rejection in kidney transplant patients converted from tacrolimus immediate-release formulations in combination with other immunosuppressants. It is administered 80% of the pre-conversion daily dose of tacrolimus immediate-release by mouth once a day. Its side effects and drug interactions are similar to the immediate-release tacrolimus.

3.5. Potential Risk and Benefits to Subjects

3.5.1. Known Potential Risks

Immunosuppressants, including extended release Envarsus XR, increase the risk of developing lymphomas and other malignancies, particularly of the skin. Other risks include, an increased risk of developing bacterial, viral, fungal, and protozoal infections, including opportunistic infections. Medication errors, including substitution and dispensing errors, between tacrolimus immediate-release products and tacrolimus extended-release products were reported outside the U.S. This led to serious adverse reactions, including graft rejection, or other adverse reactions due to under- or over-exposure to tacrolimus. Envarsus XR caused new onset diabetes after transplant (NODAT) in kidney transplant patients, which may be reversible in some patients. African-American and Hispanic kidney transplant patients are at an increased risk of NODAT. Envarsus XR, like other CNIs, can cause acute or chronic nephrotoxicity, may cause a spectrum of neurotoxicities. Other risks includes, hyperkalemia, rise in creatinine, electrolytes disturbance, hypertension, QT prolongation, drug interaction with CYP3A inducers and inhibitors. Live attenuated vaccines during treatment with Envarsus XR is contraindicated. Other post marketing experience includes- blood and lymphatic system disorders, ear disorders, eye disorders, gastrointestinal

disorders, hepatobiliary disorders, hypersensitivity reactions, immune system disorders, metabolic and nutrition disorders, musculoskeletal and connective tissue disorders, neoplasm, nervous system disorders, renal and urinary disorders, respiratory, thoracic and mediastinal disorders and skin and subcutaneous disorders. When comparing Envarsus XR with immediate release tacrolimus, potential risks were almost similar between the two groups.

Refer to the FDA approved package insert for Envarsus XR in Appendix 1.

3.5.2. Protection Against Risks

Together with the UW ICTR Data Monitoring Committee (DMC) we will develop a detailed data and safety monitoring plan (DSMP) which will ensure ongoing safety of participating patients commensurate with the level of risk and complexity of the protocol treatment to minimize risks, integrity of trial data and scientific validity of the trial. The development of the DSMP will be guided by the NIH Policy for Data and Safety Monitoring and by the FDA Guidance on the Establishment and Operation of Clinical Trial Data Monitoring Committees. The plan will make certain that review of the conduct of research is rigorous, independent and objective, interim safety and efficacy data is collected and presented and progress towards achieving study goals is made. It will cover policies and procedures for reporting adverse events to the DMC, IRB, and the FDA. Refer to Appendix 2: Data Monitoring Committee Charter and Appendix 3: Data and Safety Monitoring Plan (DSMP)

3.5.3. Potential Benefits to the Subjects

It is anticipated that the subject will benefit through early recovery of DGF, with shorter duration of dialysis treatment after transplant. This ultimately will lead to the prolonged graft survival.

3.5.4. Risk Minimization

Serious Adverse Events (SAEs) will be reviewed to determine if additional risk could be posed to the subject in question or others participating in the study. If it is determined that a serious adverse event, new information, or an unanticipated event could pose a potential risk to subjects, the DMC and/or the investigator may decide to stop the study.

4. Study Objectives and Purpose

- Primary Objective: Early recovery from DGF
- Secondary Objective: To assess the efficacy of Envarsus XR in kidney transplant recipients with DGF in achieving steady state tacrolimus levels compared to immediate release tacrolimus administration (SOC).

5. Study Design and Endpoints

5.1. General Design

This is a single center randomized phase IV trial of comparing extended release Envarsus XR once a day vs immediate release tacrolimus twice a day in a new kidney transplant recipients with DGF. The duration of study is expected to be around 2 to 2.5 years.

5.1.1. Primary Study Endpoints

The primary endpoint of the study will be the interval between first dialysis and last dialysis after kidney transplant (duration of DGF).

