5.1.3. Primary Safety Endpoints

Primary safety endpoints include: infections, malignancies, hematological complications including leukopenia, anemia, and thrombocytopenia, cardiovascular complications and events, neuropathy, tremors, gastrointestinal symptoms, uncontrolled hypertension, serious electrolytes abnormalities and immunosuppression-related adverse effects.

6. Study Subjects – Enrollment and Withdrawal

- A total of 100 subjects (50 subjects in each arm) with the diagnosis of DGF will be enrolled over a period of 2 years.
- DGF is defined as the need for a dialysis within the first week of transplant. Once potential DGF patients are identified, the transplant nephrology team will be consulted and the transplant nephrology provider will perform initial evaluation of a patient, discussion with the patient about his/her interest in participating in the research study and inform the research coordinator.
- Subjects will participate in the study until the recovery of DGF as documented by the provider as “discharged from the DGF clinic” or no need for dialysis for more than one week (7 days).
- Subject would be followed for maximum of 3 months. If they still need dialysis beyond 3 months, will be declared as primary dysfunction and will disqualify from the study.

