6.2. Inclusion Criteria

Inclusion Criteria	
1	Willing and able to provide written informed consent
2	Willing to comply with all study procedures and be available for the duration of the study
3	Male or female, at least 18 years of age
4	Documented diagnosis of DGF or need for dialysis or had dialysis within the first week of kidney transplant
5	Current treatment with tacrolimus based regimen or planned to start tacrolimus based immunosuppressive regimen
6	Females of childbearing potential must have a negative urine or serum pregnancy test prior to randomization and agree to use adequate contraception (hormonal or barrier method of birth control; abstinence) prior to randomization, for the duration of study participation, and for 7 days following completion of therapy. 
 • A female of child-bearing potential is any woman (regardless of sexual orientation, having undergone a tubal ligation, or remaining celibate by choice) who meets the following criteria: 
 ○ Has not undergone a hysterectomy or bilateral oophorectomy; or ○ Has not been naturally postmenopausal for at least 12 consecutive months (i.e., has had menses at any time in the preceding 12 consecutive months).

6.3. ***Exclusion Criteria***

Exclusion Criteria
1. History of hypersensitivity or allergy to any of the study drugs or drugs of similar chemical classes
2. Current use of non-tacrolimus based immunosuppressive regimen or no plan to start tacrolimus based regimen
3. Women who are or plan to become pregnant or breast-feeding during the study period
4. Not suitable for study participation due to other reasons at the discretion of the investigator
5. Major post-surgical complications requiring allograft nephrectomy
6. Multi-organ transplant recipients
7. Non kidney transplant recipients

6.4. ***Subject Screening for Recruitment***

6.4.1. **Subject Identification**

The screening visit will occur within the first week of transplant when transplant nephrology service is consulted for the potential need of dialysis. Basic information about the study will be provided to the patients to assess their interest to participate in the study. All of the recruitment will be performed while patient is still in the hospital after kidney transplant. The following procedures will occur as part of clinical care and will be collected from the subject's medical record:

- Physical exam

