8.2. Study Visits

8.2.1. Screening/Baseline

At screening/baseline visit transplant nephrology provider will decide about the need of dialysis or not and based on that information will document patient to have DGF or not. In that visit, we will review the patient's medical records. Patient will also be informed about the study and their interest will be gauged. If they are interested, then research coordinator will be informed about the potential subject.

Table 2. Medical chart review of standard of care visits

Visit*	Window	Data collection from medical record and Transplant Database
Day 1 contact	+/- 1 days	H&P, brief updates about research project
Day 3	+/- 0 days	H&P, decision for dialysis, decision to adjust study or SOC dose
Day 5	+/- 0 days	H&P, decision for dialysis, decision to adjust study or SOC dose
Day 7	+/- 0 days	H&P, decision for dialysis, decision to adjust study or SOC dose
Additional visits every 2-3 days until DGF recovery	+/- 0 days	H&P, decision for dialysis, decision to adjust study or SOC dose
Monthly up through Month 3 post diagnosis of DGF	+/- 30 days	H&P, decision for dialysis, decision to adjust study or SOC dose

*visits could be more or less depending upon the timing of DGF recovery for maximum of 3 months post-transplant.

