9.1. Sample Size Determination

Goal is to analyze 100 subjects total (50 in each group), with a goal to decrease DGF duration to less than 10 days in Envarsus XR group from current mean of 13.9 +/- 7 days with tacrolimus based on the power calculation.

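### The primary endpoint runs from first to last dialysis and is not tied to randomisation, so patients randomised on need and never dialysed have no value and could drop out of the analysis

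*Combined protocol and SAP*

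**What the plan says.** - **Endpoint.** Section 5.1.1: "the interval between first dialysis and last dialysis after kidney transplant (duration of DGF"). Neither randomisation nor the first study dose enters the definition.
- **Entry.** Inclusion criterion 4 (Section 6.2) has three routes joined by *or*: "Documented diagnosis of DGF or need for dialysis or had dialysis within the first week of kidney transplant".
- **DGF.** Section 6 rests the diagnosis on need, not on receipt: "DGF is defined as the need for a dialysis within the first week of transplant". In Section 8.2.1 the nephrology provider "will decide about the need of dialysis or not and based on that information will document patient to have DGF or not".
- **Timing.** Figure 1 places "Randomize into Tacrolimus (SOC) or Envarsus XR (study) group" at Visit 2, labelled as the diagnosis of DGF, after consent and baseline assessments. Section 6.4.1 adds: "All of the recruitment will be performed while patient is still in the hospital after kidney transplant". No maximum gap between first dialysis and randomisation is given.
- **Blinding.** Section 7.4: none.
- **Analysis set.** Section 9.3 uses patients who were randomised and completed. Sections 9.2, 9.3 and 10.2.4 give no rule for a duration that does not exist.
- **Planning figures.** Section 9.1: 50 per arm, a target below 10 days, and a "current mean of 13.9 +/- 7 days with tacrolimus".

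Section 9.3 also exchanges the primary and secondary labels relative to Sections 5.1.1 and 5.1.2. That is a separate matter; this point follows Sections 5.1.1 and 9.1.

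**The concern.** The endpoint behaves differently in three kinds of eligible patient.

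1. **Randomised on need, never dialysed.** There is no first or last session, so there is no value. These are patients with a good outcome. Leaving them out conditions the comparison on something that happens after assignment, and randomisation does not protect against that.
2. **Randomised on need, first dialysed later.** The clock starts after assignment, at a session timed by clinicians who know the arm. A later first session shortens the interval even if recovery comes on the same day.
3. **Dialysed before randomisation.** Part of the interval is fixed before assignment, and all of it if the last session was already past. Randomised treatment cannot change those days.

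The first two are possible routes to bias. The third is a matter of precision.

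**Working it through.** **Inputs.** From Section 9.1: control mean 13.9 days, SD 7 (reading +/- 7 as an SD), target 10 days, 50 per arm. From Section 9.2: significance level 0.05. Assumed because the plan does not state them: a two-sided test and 80% power.

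**Step 1: the plan's own figure.** The difference is 13.9 − 10 = 3.9 days. By the normal approximation, n per arm = 2 × 7² × (1.960 + 0.842)² / 3.9² = 50.6, rounded up to 51, against 50 stated. The sample size therefore reproduces, and the point does not rest on an arithmetic error. With 50 per arm the noncentrality is 3.9 / (7 × √(2/50)) = 3.9 / 1.4 = 2.786 on 98 df, and power by the noncentral t is 78.8%. The normal approximation gives 79.6%; the t figure is used in Steps 2 and 3.

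**Step 2: cost of the days before randomisation.** Assume that the lag from first dialysis to randomisation is uniform over 0 to w days and independent of the days that follow. Its variance is w²/12, and the SD without it is √(49 − w²/12). The 3.9-day difference is held fixed.

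| w (days, assumed) | Lag variance | Remaining SD | Power, 50 per arm |
|---|---|---|---|
| no removal | – | 7.00 | 78.8% |
| 2 | 0.33 | 6.98 | 79.0% |
| 3 | 0.75 | 6.95 | 79.4% |
| 6 | 3.00 | 6.78 | 81.2% |
| 7 | 4.08 | 6.70 | 82.1% |

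The gain is under one percentage point for a short lag and two to three points for a long one. It comes from removing the lag variance. Adjusting the existing first-to-last interval for the lag would remove the same variance.

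**Step 3: cost of dropping never-dialysed patients.** The share is assumed, and the difference and SD are held at 3.9 and 7 among those who remain.

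| Share dropped (assumed) | n per arm | Noncentrality | Power |
|---|---|---|---|
| 0% | 50 | 2.786 | 78.8% |
| 5% | 47.5 | 2.715 | 76.6% |
| 10% | 45 | 2.643 | 74.3% |

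This counts only the lost numbers. The bias from the selection cannot be sized from the documents.

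**Step 4: no arithmetic applies to the start of the clock.** Sections 5.1.1, 6.2 and 7.4 together allow a start point that follows assignment in an open trial. They give no information on how often this happens or whether the arms would differ.

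**The case against.** First-to-last dialysis is a natural measure of DGF duration and the scale of the planning figures. Screening takes place when nephrology is consulted about a possible need for dialysis (Section 6.4.1), and randomisation is at the visit labelled as the diagnosis of DGF. Both suggest randomisation close to first dialysis, so the lag may be short and its removal worth little. Never-dialysed patients may be rare, because a provider has already judged dialysis to be needed. The documents show no mechanism by which assignment would move a first session already judged necessary. A new origin also has no documented mean or SD.

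All of this stands as to size. It does not supply the missing value for a patient whom the entry criteria plainly admit, nor say that such a patient stays in the analysis.

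Three stronger readings are tempting but not supported:

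- **That the pre-randomisation days bias the comparison.** They are fixed before a 1:1 assignment and balanced in expectation. They also arise only in patients dialysed before randomisation, and they precede randomised treatment only, not all tacrolimus: "All subject will receive at least one dose of SOC tacrolimus" (Section 1).
- **That the endpoint's origin costs a large part of the power.** If the planned 28% reduction (3.9 / 13.9) could act only on days after randomisation, lags of 1 to 3 days would shrink the difference to 3.62–3.06 days and power to about 73–59% (normal approximation, from 79.6%). But that difference in days is the same from either origin, so re-timing would not recover the loss.
- **That many patients will lack a value.** No passage gives a number.

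**Conclusion.** The point holds as a gap in the endpoint definition that should be closed. What matters most is the undefined value for patients randomised on need and never dialysed, because Section 9.3 makes their exclusion a natural reading and that exclusion would depend on outcome. Next is the post-randomisation start of the clock in an unblinded trial, a weakness whose effect cannot be quantified. The days before randomisation matter least.

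In figures, power moves from 78.8% to between 79.0% and 82.1% if the lag is removed, and to between 76.6% and 74.3% if 5–10% of patients are dropped. These results rest on the assumed lag distribution, its independence of later days, the assumed share, a two-sided test, and SD 7. The conclusion rests on the wording of the definition and not on any one of these figures.

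**What to change.** 1. Analyse all randomised patients, and bring Section 9.3 into line with this.
2. Define the primary endpoint as days from randomisation to last dialysis, up to 3 months after transplant. Score 0 for patients alive with a functioning graft and no dialysis after randomisation.
3. State separately how death and graft loss are scored, so that neither receives the best value.
4. Adjust for days from first dialysis to randomisation (0 if none), with an indicator for dialysis before randomisation. The indicator separates patients first dialysed on the day of randomisation from those not yet dialysed.
5. Keep first-to-last dialysis as a supportive endpoint, with never-dialysed patients scored 0, so that the result can still be set against 13.9 days.

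If the sponsor prefers to keep first-to-last as primary, the minimum is to score never-dialysed patients 0, keep them in the analysis, and adjust for the pre-randomisation days. That leaves the post-randomisation start of the clock in place.

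**Cost.** No added visits, patients or procedures: dialysis decisions and intervals are already collected (Figure 1, Section 8.2.1), and randomisation dates necessarily exist. The primary number is no longer the conventional interval, a regression model replaces the simple two-group test of Section 9.2, and the mean and SD in Section 9.1 must be checked on the new scale.
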